11. MEASUREMENT OF EFFECT

11.1 Primary Endpoint: Proportion free of radiographically evident metastases at 18 months. Bone scans with <3 metastatic lesions should be confirmed with CT/MRI or a repeat scan >4 weeks after the initial scan. Should a subject require confirmatory scans, the date of radiographic progression will be the date of the initial scan showing suspicion of metastasis.

11.1.1 Metastasis-free survival

Time to development of metastatic disease will be calculated from the date of treatment to the date of the first radiographic evidence of metastatic disease. Bone scans with <3 metastatic lesions should be confirmed with CT/MRI or a repeat scan >4 weeks after the initial scan. Should a subject require confirmatory scans, the date of radiographic progression will be the date of the initial scan showing suspicion of metastasis.

11.2 Response Criteria

11.2.1 Biochemical (PSA) response

A PSA decline of $\geq 50\%$ has been demonstrated to correlate with improved survival in advanced castrate disease (119). In addition, Scher, et al have demonstrated that a PSA which either declines or shows no increase from baseline at either 8 or 12 weeks after initiating therapy correlates with improved survival compared to patients whose PSA rises despite therapy (120). Both of these criteria ($\geq 50\%$ PSA decline and no increase from baseline) will be recorded.

PSA response will be determined by comparing the PSA levels after therapy to the baseline, pre-treatment PSA. A decline of $\geq 50\%$, confirmed by a second PSA value ≥ 2 weeks later, should be reported. Patients must not demonstrate clinical or radiographic (CT and/or MR) evidence of disease progression during this time period.

Analyses of phase III trials of docetaxel versus mitoxantrone chemotherapy in men with metastatic androgen independent prostate cancer have shown that a 30% decrease in PSA levels is most strongly associated with a treatment effect on overall survival (52, 53). A PSA decline of $\geq 30\%$ will be assessed and used for exploratory analysis in the prediction of time to metastatic disease and overall survival.

11.2.2 Duration of PSA response

Duration of PSA response is defined as the time from the first 50% (or 30%) PSA decline until the PSA value is confirmed to increase by 25% above the nadir, provided that the increase is at least 2 ng/mL above nadir.

11.2.3 Progression (see also 11.1)

11.2.3.1 Biochemical progression

Biochemical (PSA) progression is defined as a PSA measured ≥ 12 weeks after treatment which is confirmed (by a repeat assay) to rise $\geq 25\%$ above the baseline, pre-treatment value AND ≥ 2 ng/mL. In the case of a patient whose PSA declines after therapy, PSA progression is defined as a rise in PSA $\geq 25\%$ above the nadir value AND ≥ 2 ng/mL. The time of progression is determined using the date of the 1st (subsequently confirmed) PSA $\geq 25\%$ above baseline or nadir. PSA rise < 12 weeks of initiating treatment is not considered to be progression.

11.2.3.2 Time to biochemical progression

Time to PSA progression is defined as the interval between initiating treatment until the PSA rises 25% above nadir provided that the increase is at least 2 ng/mL

11.2.3.3 Time to PSA progression above baseline

Time to PSA progression above baseline will also be recorded. Time to PSA progression above baseline will be defined as the interval between initiating treatment until the PSA rises above the pre-treatment baseline by at least 2 mg/mL. PSA rise < 12 weeks of initiating treatment is not considered to be progression.

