3.1.2 Biochemical progression (rising PSA) after medical or surgical castration

- Subjects who have received antiandrogens (such as bicalutamide) and have experienced PSA decline must have biochemically (PSA) progressed following discontinuation of anti-androgen therapy.
- **PSA:** An increase in PSA determined by two separate measurements taken at least one week apart and confirmed by a third, and if necessary, a fourth measurement. If the third measurement is not greater than the second measurement, then a fourth measurement must be taken; the fourth measurement must be greater than the second measurement for the patient to be eligible for enrollment in the study. Furthermore, the confirmatory PSA measurement (i.e., the third or, if applicable, fourth PSA measurement) must be ≥ 1 ng/mL with prior prostatectomy or ≥ 2 ng/mL without prostatectomy and $\geq 25\%$ above the previous nadir.

3.1.3 High risk of systemic progression defined as:

- Rising PSA as defined above and either:
 - Absolute PSA > 20 ng/mL
AND/OR
 - PSA DT < 8 months

PSA doubling time (PSA-DT) will be calculated using a linear regression model. In the model, the logarithm of PSA will be modeled as a linear function of time. The PSA-DT will be calculated as the product of $\log 2$ multiplied by the reciprocal of the slope of the regression equation, for which the logarithm is the natural log function. For standardization purposes across sites, a web-based PSA doubling time calculator developed by Memorial Sloan Kettering, is available at <http://www.mskcc.org/mskcc/html/10088.cfm>

The minimum PSA value for eligibility will be greater than or equal to 1 with prior prostatectomy or at least 2 ng/mL without prostatectomy. All PSA values of at least 0.1 ng/mL over the past 6 months must go into the equation. A minimum of 3 PSA values with a minimum of 2 weeks between assessments is required (the screening PSA may be used for the 3rd value if necessary).

- 3.1.4 No evidence of local recurrence or distant metastases within 1 month of enrollment (or following enrollment as part of screening) including:
 - Radionuclide bone scan without evidence of metastatic disease
 - In the event of an equivocal bone scan, confirmation is needed with Xray, CT scan, or MRI
 - CT or MRI of abdomen/pelvis without evidence of metastatic disease or recurrent disease in the prostate or prostate bed

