13.4 Analysis of Secondary & Exploratory Endpoints

Secondary endpoints include biochemical (PSA) response rate, duration of PSA response, biochemical (PSA) progression, time to biochemical (PSA) progression, time to biochemical (PSA) progression above baseline, overall survival, and toxicity. We anticipate that the 95% confidence interval around the PSA response rate will be within $\pm 9\%$ of the true value for Arm 1 and within $\pm 15\%$ of the true value for Arm 2. Time to biochemical (PSA) progression, time to biochemical (PSA) progression above baseline, median MFS-time, and overall survival will be estimated using the Kaplan-Meier method, and 95% confidence intervals will be calculated using Greenwood's formula.

The frequency of subjects experiencing toxicities will be tabulated. Toxicities will be assessed and graded according to CTCAE v. 4.0 terminology. Exact 95% confidence intervals around the toxicity proportions will be calculated to assess the precision of the obtained estimates.

Imaging studies: The possibility of identifying sites of metastatic disease not apparent on conventional imaging (CT/MRI abdomen/pelvis, bone scan, and CXR) will be confirmed with serial imaging. Any potential metastatic site on J591 imaging will be followed over time by conventional imaging. Sites of disease appearing on J591 scan and subsequently confirmed by conventional imaging will be labeled as positive. Any site apparent on J591 scan that is subsequently biopsied as part of standard care and confirmed to be metastatic prostate cancer will be labeled as definite. Sites of disease appearing on J591 scan without any corroborating evidence (conventional imaging or biopsy) will be labeled as possible.

Adrenal hormonal levels: Baseline adrenal hormonal levels will be categorized by median baseline levels found in CALGB 9583 (60, 61). In addition, as this may be a different patient population, we will analyze by median as well as quartiles. We will correlate levels with time to radiographic metastatic disease as well as PSA response and overall survival. Changes in adrenal hormone levels will be analyzed with time (baseline, 1 month, 6 months, at progression).

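### Time to PSA progression above baseline rests on a fixed, unconfirmed rise of 2 units (printed as mg/mL), looser than the plan's own 25% rule for every baseline above 8 ng/mL

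*Combined protocol and SAP*

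**What the plan says.** Section 11.2.3.3 defines time to PSA progression above baseline as "the interval between initiating treatment until the PSA rises above the pre-treatment baseline by at least 2 mg/mL". The only other condition there is that a "PSA rise < 12 weeks of initiating treatment is not considered to be progression".

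The two neighbouring definitions are stricter. Against the same baseline, section 11.2.3.1 asks for a rise of at least 25% "above the baseline, pre-treatment value AND ≥ 2 ng/mL", and the PSA must be one that "is confirmed (by a repeat assay) to rise" by that amount. Section 11.2.3.2 runs "until the PSA rises 25% above nadir provided that the increase is at least 2 ng/mL". Both give the unit as ng/mL.

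Section 3.1.3 makes "Absolute PSA > 20 ng/mL" one of two high-risk entry criteria, joined by and/or to a PSA doubling time under 8 months, and sets no upper limit on PSA. Section 13.4 lists the endpoint among the secondaries ("time to biochemical (PSA) progression above baseline, overall survival, and toxicity") and plans its analysis: "time to biochemical (PSA) progression above baseline, median MFS-time, and overall survival will be estimated using the Kaplan-Meier method".

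**The concern.** Three things are wrong with the definition as printed: the unit, the missing percentage condition and the missing confirmation. The protocol gives no reason for dropping the last two, which section 11.2.3.1 applies to the same baseline.

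A fixed 2 ng/mL is a small relative change at a high baseline, and men with a high baseline are enrolled by design. PSA is measured about every 4 weeks on ketoconazole, so a man whose PSA sits near baseline has repeated chances to cross a small threshold once.

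The protocol would also give two answers on the same values. Take a man with baseline 40 ng/mL whose PSA never fell and who reads 43 at week 16. He has progressed above baseline under section 11.2.3.3, which needs 42, but not under section 11.2.3.1, which needs 50. What is at stake is whether the Kaplan-Meier curve for this endpoint describes progression.

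**Working it through.** The plan gives no figure for this definition, so there is nothing to reproduce. The check has four steps.

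**1. The unit.** 2 mg/mL = 2,000,000 ng/mL. No patient would reach it. From here the unit is read as ng/mL, as in sections 11.2.3.1 and 11.2.3.2.

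**2. Relative size of the threshold.** The required rise is 2/B for baseline B. It equals 25% when B = 2/0.25 = 8 ng/mL and is smaller for every higher baseline.

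| Baseline (ng/mL) | +2 as % of baseline | Rise needed under 25% and 2 ng/mL |
|---|---|---|
| 8 | 25% | 2 |
| 20 | 10% | 5 |
| 40 | 5% | 10 |
| 50 | 4% | 12.5 |
| 100 | 2% | 25 |

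This step needs no assumption beyond the unit. The 2 ng/mL in section 11.2.3.1 is read as an increase, which is how section 11.2.3.2 words it.

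**3. False events when nothing changes.** The documents give no within-man PSA variability, so the CV is an assumption, shown at 5%, 10% and 15%. True PSA is held flat at baseline. One baseline value and four values after week 12 carry independent log-normal variation. An event is any value at or above measured baseline + 2. Confirmation means two consecutive qualifying values within the four visits.

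| Baseline | Rule | CV 5% | CV 10% | CV 15% |
|---|---|---|---|---|
| 25 | +2, unconfirmed (as written) | 33% | 58% | 67% |
| 40 | +2, unconfirmed (as written) | 51% | 67% | 72% |
| 100 | +2, unconfirmed (as written) | 70% | 75% | 77% |
| 25 | +2, confirmed | 9% | 25% | 32% |
| 40 | +2, confirmed | 20% | 34% | 39% |
| 100 | +2, confirmed | 37% | 43% | 46% |
| 25 to 100 | 25% and 2, confirmed | under 0.1% | about 3% | about 11% |

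At baseline 5 and CV 10% the rule as written gives about 1%.

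A separate run with six visits, each value confirmed by the next, points the same way. At baseline 20 and CV 10%, 61% falls to 29% with confirmation alone, 21% with the 25% condition alone and 5% with both. Each condition does part of the work.

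**4. Real regrowth.** With an assumed 5-month doubling time, PSA reaches baseline + 2 at 5 × log2(1 + 2/B) months after it passes baseline: 0.56 months at B = 25 and 0.14 at B = 100. It reaches 25% above baseline at 5 × log2(1.25) = 1.61 months. The stricter rule therefore dates the event later by 1.61 − 0.56 = 1.05 months at 25 and 1.61 − 0.14 = 1.47 months at 100.

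**The case against.** The flat-PSA case is the worst case. Men enter with a rising PSA and all start secondary hormonal treatment, so many will fall well below baseline or keep rising. Take a man at 50% of baseline at week 12 who regrows with a 5-month doubling time, CV 10% and 4-weekly visits. Events at week 12 are then essentially nil, and the median event time is 8.3 months against a true baseline crossing at 7.8 months. Across declines of 30% and 50%, some 10% to 32% of events precede the true crossing. That is a shift in date rather than false progression. This stands, and it limits the point to men hovering near baseline. The documents do not say how many there will be.

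The endpoint may also be meant as a simple marker of PSA returning past its starting level, separate from section 11.2.3.1. That is possible, but the protocol does not say so, and the unit would still need correcting.

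A reader might infer more than the documents support:

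- That ordinary PSA noise will in fact be counted as progression. This depends on an assumed CV.
- That an arm difference is diluted. Section 13.4 states no between-arm test for this endpoint, and the definition is the same in both arms.
- That the 25% condition would also mend late events in men with low PSA. A baseline of 1.5 ng/mL needs a rise of 2/1.5 = 133% under either rule. Below 8 ng/mL the 25% condition changes nothing.
- That follow-up is affected. The switch to 3-monthly scans is tied to PSA (biochemical) progression, which section 11.2.3.1 defines, and a rising PSA alone does not end participation.

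**Conclusion.** The point holds as a defect in one secondary endpoint definition. Two parts need no assumption about PSA variability: the printed unit makes the event unreachable, and in ng/mL the threshold is looser than 25% for every baseline above 8 and below 10% for every man above 20. The same values can therefore count as progression above baseline in one section and not in the next.

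The size of the false-event problem is conditional. With true PSA flat over four visits and an assumed CV of 5% to 15%, it is 33% to 67% at baseline 25 and 70% to 77% at baseline 100. These rates describe men whose PSA stays near baseline after week 12. They do not forecast the share of the trial population that would be misclassified. In men who fell and regrew, the effect is mainly on the date. The primary endpoint, the proportion free of metastases at 18 months, is untouched.

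**What to change.** In section 11.2.3.3, correct the unit to ng/mL. Define the event as a rise of at least 25% and at least 2 ng/mL above the pre-treatment baseline, confirmed by a repeat assay and dated at the first of the confirming values, as section 11.2.3.1 already does against baseline. Keep the week-12 floor. If a different rule is intended, state it with the right unit and say why it differs. Settle this before the endpoint is analysed.

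The change is a sentence and uses PSA values that are already scheduled. Confirmation alone is not enough: at CV 10% it leaves 25% to 43% across baselines 25 to 100, against about 3% with both conditions. The cost is later dating of real rises in men with high PSA, by about 1 to 1.5 months at an assumed 5-month doubling time. Below 8 ng/mL the size of rise required does not change; only confirmation is added.

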12. DATA REPORTING / REGULATORY CONSIDERATIONS

12.1 Data Collection and Monitoring

The data collection plan for this study is to utilize a user ID/password protected encrypted database created by the WCMC CTSC to capture all treatment, toxicity, and efficacy data for all enrolled patients. Electronic CRF's (case report forms) utilizing unique study ID numbers to minimize potential exposure of PHI will be completed on an ongoing basis by all sites.

The study will be monitored by Weill Cornell Medical College. Data integrity will occur via electronic and fax queries. A review of the majority of source documents to verify CRF integrity is planned for the initial subject treated at each site. Further electronically collected data will be reviewed in real time and electronic queries will be sent. Weill Cornell reserves the right to site audits as necessary. In the event this will occur, the site will be given ample notice prior to the visit.

12.2 Regulatory Considerations

All protocol amendments and consent form modifications will be made by the Study Chair. Weill Cornell will have the opportunity to review and approve the changes prior to submission of these changes to the Weill Cornell IRB and distribution to participating sites.

12.3 Data Safety Monitoring Board

This study will utilize the Weill Cornell Medical College (WCMC) Institutional Data Safety Monitoring Board (DSMB) and follow its policies and procedures for monitoring this double-blinded study for safety concerns, with ongoing updates from the Study Chair on an ongoing basis. The interim analysis will be performed by the DSMB and the decision to proceed or stop the trial will be provided to the Study Chair.

The Weill Cornell DSMB is comprised of medical specialists and advisors on human rights issues in human subjects research. The DSMB currently has 9 members, meets at quarterly intervals during the year, and carries out ongoing review of protocols submitted throughout the year. Once a protocol has been submitted and approved by the Institutional Review Board (IRB) and is recommended for oversight by the DSMB, the Board determines if the protocol will be reviewed quarterly, semi-annually, or annually.

The DSMB evaluates the accumulated data from the study in order to monitor the safety of subjects throughout the trial and reviews the risks and benefits, as well as the efficacy, of the study. The DSMB will also evaluate the overall trial conduct and progress. Ultimately, the DSMB validates the continuation of the trial or determines if a study needs modification or termination.

Reports to the DSMB will include the following items for review:

1. Completed DSMB Periodic Review Form.
2. Synopsis of the study to date.
3. IRB approved consent form.
4. IRB current protocol.
5. Summary table of study results.
6. Adverse event table.
7. Data safety monitoring plan.

Safety monitoring is carried out to ensure and maintain the scientific integrity of human subject research projects and to protect the safety of human subjects. Safety

monitoring can be viewed as any process during a clinical trial that involves the review of accumulated outcome data for groups of patient-subjects to determine if any of the treatment procedures practiced should be altered or stopped. NIH Guidelines (1998, 2000) specify that all clinical trials should have a system in place for appropriate oversight and monitoring to ensure the safety of participants and the validity of the data.

Monitoring activities will be commensurate with the nature, size, and complexity of the trial in accordance with institutional policies and will be determined after IRB and DSMB review of the protocol immediately prior to study activation. For a small, single-center study, the monitoring is usually performed by a statistician in conjunction with a Safety Officer. For those single-site, high risk trials, a DSMB may be appropriate. For larger, single or multi-site studies, the monitoring is usually performed by a committee, often called a Data Safety Monitoring Board (DSMB). Ongoing review of the data by an independent individual or committee assures the investigators, the IRB, the study's sponsor, and the funding agency that the trial can continue without jeopardizing subjects' safety.

Weill Cornell Medical College requires that all research approved by the WCMC IRB include an appropriate plan for the monitoring of data to ensure the safety of human subjects. Research supported by Federal agencies will be monitored according to all regulations and guidelines of the relevant Federal agency.

12.4 Initial Safety Review

¹⁷⁷Lu-J591 has been shown to be safe at a dose of 70 mCi/m² in a phase I dose-escalation trial and a multicentered phase II trial. Because the major toxicity (myelosuppression) is at least in part due to the location of metastases (cortical bone and bone marrow), it is expected that the toxicity in this study population will not exceed that seen in the trials in metastatic CRPC. However, safety data will be monitored on a real-time basis by the Study Chair and shared with the core study investigators. Should there be > 1 subject experiencing a stopping rule as defined by agreement with the FDA during the conduct of the phase II trial in metastatic CRPC (see Appendix B) within the initial 9 subjects (approximately 6 subjects receiving ¹⁷⁷Lu-J591), enrollment will be halted pending DSMB review. Enrollment will continue without a pause during the ongoing safety analysis. Completion of initial safety review is anticipated to be completed in summer, 2011.

12.5 Analysis and Data Reporting

Secondary endpoints examining the patient population or treatment with ketoconazole/hydrocortisone without regard to the study drug (radiolabeled J591) may be analyzed without breaking the blinding procedures on an ongoing basis and may be reported during the conduct of the study.

13. STATISTICAL CONSIDERATIONS

13.1 Study Design/Endpoints

The study is a randomized phase 2 study with a 2:1 ratio favoring ^{177}Lu -J591, with stratification by investigational site and mode of primary therapy (radiation vs surgery). Randomization will be performed by using a series of randomized blocks of 6 within each participating site/primary therapy stratum (with a 2:1 allocation ratio). This will provide assurance that after six patients are enrolled in any given participating site/primary therapy stratum, there will be four patients assigned to the combination regimen (Group 1) and two patients assigned to the single regimen (Group 2). This procedure will allow for each site to contribute similar numbers of ^{177}Lu -J591/ketoconazole patients and ^{111}In -J591 (placebo)/ketoconazole patients within the defined participating site/primary therapy strata.

The primary endpoint is the proportion free of metastases in each group at 18 months. Ninety-five percent confidence intervals (95% CI) will be estimated for the 18-month MFS proportion in both groups via binomial proportions. The MFS proportion will also be descriptively evaluated at 12, 24, 30, and 36 months in each group.

MFS will be measured from the start of the treatment to the date of either documentation of metastatic disease or death. All treated patients will be observed for a minimum of 18 months. The 18-month MFS proportion with ketoconazole + ^{111}In -J591 has been estimated to be 50% {521 Smith, M.R. 2005}; therefore, the target 18-month MFS proportion for the combination of ketoconazole + ^{177}Lu -J591 regimen is hypothesized to be 80%. An intent to treat analysis will include all randomized subjects. However, we will also analyze subjects who received study-drug. This subset will be those subjects who met eligibility requirements, have initiated therapy, and were not removed from the study for non-compliance or patient withdrawal within the first 4 weeks, and received infusion of study drug.

With approximately 34 patients in the ketoconazole+J591 arm and 17 patients in the ketoconazole monotherapy arm (2:1 allocation), this design will allow for the detection of a 30% absolute difference in the 18-month MFS proportion between the ketoconazole+J591 arm and the ketoconazole monotherapy arm (80% vs. 50%, respectively) with $\geq 80\%$ power and a one-sided alpha level of 10%. An additional 10% will be enrolled to account for loss to follow up (total projected number of subjects to be randomized = 55). A 95% CI for the difference in the 18-month MFS proportion between the two treatment arms can be constructed to be within $\pm 18\%$ of the true difference in 18-month MFS proportions.

13.1.1 ^{111}In -J591 as placebo

We have chosen to infuse ^{111}In -J591 as a placebo in this double-blind study. The infusion procedures and characteristics of this compound are similar to ^{177}Lu -J591. In addition, ^{111}In -J591 will allow imaging studies to be performed. Because ^{111}In is a pure gamma-emitter, there will be no treatment effect as in the beta emission with ^{177}Lu . It is theoretically possible that by infusing ^{111}In -J591, there will be a treatment effect by ADCC, thereby diluting the proportional effect of ^{177}Lu -J591 in the experimental arm. However, clinically meaningful ADCC is not expected, as it has been demonstrated at

much higher doses of the J591 antibody (122), and by giving equal antibody doses in each study arm, we will be able to truly evaluate the effect of ^{177}Lu radioimmunotherapy.

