Platelet nadir <25 x 10⁹/L occurred in 42% of pts, 9 of whom required 1 – 4 platelet transfusions (median = 2). 29/32 pts recovered normal platelet counts; the remaining 3 pts had rapidly progressive disease with bone marrow involvement. Neutropenia ≤ 0.5 x 10⁹/L occurred in 27% of pts, 6 of whom received brief therapy with growth factors. All 32 pts had normal neutrophil recovery and no pt experienced neutropenic fever. No significant drug-related non-hematologic toxicity has occurred. Excellent targeting of known sites of PC metastases has been observed in 31/32 (97%) of pts.

In summary, single dose ¹⁷⁷Lu-J591 demonstrates anti-tumor activity in pts with progressive CRPC with reversible myelosuppression. 32 of the initially planned 32 subjects have been treated to date and follow up is ongoing. Because of an FDA mandate, treatment was begun at a lower dose than the phase I MTD. Since there appears to be a dose response relationship (13 vs 47% with >30% PSA decline, 46 vs 71% with any PSA decline), an expansion protocol at the MTD is planned to tighten the confidence intervals for response at the MTD. Based upon acceptable toxicity in both groups and signals for increased efficacy at the higher dose (the MTD based upon the phase I trial), we are proceeding with the current trial.

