13.2 Sample Size/Accrual Rate

The planned sample size is 55 subjects ($50 + 10\%$ for in-evaluable / loss to follow-up = 55). Subjects who come off protocol prior to day 29 of treatment (i.e. prior to infusion of study drug) will be replaced. It is anticipated that the average site will pre-screen several subjects per month and enroll approximately 3 subjects per year.

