13.3 Stratification Factors

Patients will be stratified by treating institution and delivery of primary therapy (surgery and/or radiotherapy vs no primary therapy to the prostate).

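### The protocol prints a fixed block size of 6 within site strata while cytopenias can hint at earlier arms, so the next assignment is partly predictable; exposure is modest and falls mainly on higher-accruing strata

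*Combined protocol and SAP*

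**What the plan says.** Section 13.1 sets out the allocation in full: "Randomization will be performed by using a series of randomized blocks of 6 within each participating site/primary therapy stratum", with 2:1 allocation. It adds that once six men have entered a stratum, "there will be four patients assigned to the combination regimen (Group 1) and two patients assigned to the single regimen (Group 2"). Every site that holds the protocol therefore knows the block size, its composition and the stratum within which it runs.

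The trial is described as double-blind, with 111In-J591 as placebo (section 13.1.1). Section 7.1.1 says that radiolabeled J591 is likely to lower platelets and/or neutrophils, and its heading expects no additional risks from 111In-J591. In the earlier phase II trial in metastatic disease, a platelet nadir below 25 x 10^9/L "occurred in 42% of pts", and neutrophils at or below 0.5 x 10^9/L were seen in 27% (section 2.1). Section 5.2.2.1 puts the platelet nadir 4-5 weeks after infusion. Section 10.1 has sites obtain the cycle 3 blood counts and submit them within 24 hours. Section 13.2 expects the average site to "enroll approximately 3 subjects per year".

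No section varies the block size, withholds it from sites, or separates staff who see blood counts from staff who enrol.

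**The concern.** A printed block size does harm only if earlier assignments can be guessed. Here there is a route to guessing them, because one infusion is expected to depress blood counts, the other is not, and the site handles the counts. An investigator who suspects the arms of earlier men in a stratum can work out better odds for the next one. The choice or timing of the next enrolment could then depend on the expected arm.

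The comparison at stake is the primary one, 18-month MFS, with about 17 men in the control arm. A few steered enrolments could matter, and selection on prognostic features that are not recorded cannot be adjusted for afterwards. The issue is predictability of the next assignment, not numerical balance between the arms.

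**Working it through.** **The plan's own figure.** Section 13.1 claims at least 80% power for 80% versus 50% MFS with 34 and 17 men at one-sided 10%. The pooled proportion is (34 x 0.8 + 17 x 0.5)/51 = 0.70. The null SE is sqrt(0.70 x 0.30 x (1/34 + 1/17)) = 0.136, and the alternative SE is sqrt(0.16/34 + 0.25/17) = 0.139. Then z = (0.30 - 1.282 x 0.136)/0.139 = 0.90, so power is 0.816. The claim reproduces, and nothing below changes it.

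**Timing.** Infusion comes about 4 weeks after the start of ketoconazole, and the nadir 4-5 weeks later, so about week 8-9. At 3 men per site per year, a site enrols one man about every 4 months. Taking randomization to be close to enrolment, the previous man's counts are usually known first.

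**Upper bound: every earlier arm in the stratum is known.** A block of four 177Lu and two 111In has 15 orderings. The next assignment is certain once either arm is used up.

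| Position | Orderings that make it certain | Share |
|---|---|---|
| 1, 2 | 0 | 0% |
| 3 | 1 of 15 | 7% |
| 4 | 3 of 15 | 20% |
| 5 | 6 + 1 = 7 of 15 | 47% |
| 6 | 15 of 15 | 100% |

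The sum is 26/15 = 1.73 per completed block, or 29% of six. But 55 men over 10-16 sites and two therapy levels is 55/32 = 1.7 to 55/20 = 2.75 men per stratum, so most strata stop early. Simulating 55 men with an assumed 60/40 therapy split gives:

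- even accrual: 2.0 of 55 (16 sites) to 4.6 of 55 (10 sites) certain, or 4-8%;
- skewed accrual (assumed: one site with 40% of men, or accrual proportional to 1/rank): 10-13%.

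Sections 13.1 and 13.3 define the therapy stratum differently: 13.1 contrasts radiation with surgery, and 13.3 has "surgery and/or radiotherapy vs no primary therapy to the prostate". If nearly all men fell in one level under the second definition (an assumption), the same bound would be about 11-19%.

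**Low case: only a severe count identifies 177Lu, and a normal count never proves 111In.** Certainty then needs all four 177Lu men detected before the next assignment. With detection probability s, the expected number per completed block is (1/15 + 5/15) x s^4 = 0.4 s^4. Fifty-five men make at most 55/6 = 9.2 completed blocks.

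| s | Certain per block | At most, in 55 men |
|---|---|---|
| 0.42 | 0.012 | 0.1 |
| 0.70 | 0.096 | 0.9 |
| 0.90 | 0.26 | 2.4 |

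The two severe signals together cover between 42% and 42 + 27 = 69% of men, so 0.70 is about their ceiling. Odds still shift without certainty: a man with no severe thrombocytopenia has a chance of being on 111In of (1/3)/((1/3) + (2/3) x 0.58) = 46%, up from 33%.

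**What it could do to the primary test.** This is a worst case: sites know all earlier arms, always act on the odds, and true MFS is 50% in both arms. With a 50/50 therapy split, if the man enrolled has his MFS probability moved by 0.10 in the favoured direction, the simulated bias is 2.6-4.7 points and one-sided type I error is 14-17%, against 10-11% with no steering. With one therapy level only, the figures are 4.7-6.4 points and 17-21%. The shift of 0.10 is an assumption; the documents give no such figure.

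**Would mixing blocks of 3 and 6 help?** Suppose both sizes are equally likely and sites know it. After two 177Lu men, the chance of a third is (0.5 x 0.4 x 0.5)/(0.5 x 1/3 + 0.5 x 0.4) = 27%, against 50% with fixed blocks of 6. The best guess for the third man is then right with probability 0.267 + 0.533 + 0.033 = 83% (summing over two 177Lu, one of each, and two 111In before him), against 0.20 + 0.40 + 0.067 = 67% with fixed blocks of 6. A known 3/6 mix is worse at exactly the positions that most strata reach.

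**The case against.** A reader might infer that blood counts reveal the arm, that sites can generally foresee assignments, and that the primary comparison is biased as a result. The documents do not support any of these.

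On detection, fewer than half of the men in the earlier trial had severe thrombocytopenia. They had metastatic disease and were pooled over two dose cohorts. Section 12.4 attributes myelosuppression partly to metastases in bone and marrow and expects toxicity here to be no worse; this trial excludes men with metastases. Milder falls were probably more common than 42%, since section 2.1 speaks of platelets recovering to normal in 29 of 32 men, but no rate is given that would identify an arm.

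On foresight, with even accrual about 62-77% of men occupy positions 1-2, where nothing is ever certain. With full knowledge the best guess over positions 1-3 is still right only two times in three, the same as always guessing 177Lu.

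On discretion, registration is central and needs source documents that verify eligibility (section 4.2), and the coordinating center arranges and ships doses (section 8.2). On repair, adjustment for measured baseline factors could partly address an imbalance.

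All of this limits the size, and it stands. It does not remove the route. Central registration does not hide the block scheme or control which pre-screened man is put forward and when. Section 13.2 expects several men pre-screened per month against about three enrolled per year, and Appendix E leaves equivocal lesions to investigator judgement. Shifted odds can bias selection without certainty.

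**Conclusion.** The block scheme is disclosed to sites, there is a plausible route to suspecting earlier arms, and no safeguard is stated. Selection bias in the 18-month MFS comparison is possible and unmitigated; the documents do not establish that it would occur.

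The expected exposure is modest and concentrated in higher-accruing strata. With full knowledge of earlier arms and the strata of section 13.1, about 4-8% of assignments are certain under even accrual and up to about 13% under skewed accrual. If only the documented 42% signal counts, almost none are certain, though the odds still move. The true position lies between these, and where depends on detection, accrual skew and the therapy split, none of which the documents give. Bias further requires sites to act on the odds and to select on prognosis. The case for change rests on the very low cost of closing the route.

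**What to change.** Delete the block size and the sentence giving the split after six patients from the site-facing protocol, keeping the 2:1 ratio and the stratification factors. Hold the block scheme in a restricted randomization document that sites and enrolling staff do not see, and let it use one definition of the therapy stratum, reconciling sections 13.1 and 13.3.

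Block sizes may be varied in multiples of 3, which keeps 2:1, but only if the sizes are withheld; the gain comes from concealment, and a 3/6 mix that sites know would make the third assignment in a stratum easier to guess. Where sites already hold the printed size, deletion alone does not undo that knowledge, so later blocks would need undisclosed sizes.

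The cost is a text amendment, a restricted document and, if sizes change, a new list. It adds no patients, visits or procedures. The planned 55 men and the power of 0.816 for 34 versus 17 are unchanged.
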